10.2 Patient demographics/other baseline characteristics

Demographic and other baseline data (including disease characteristics) will be listed in detail.

Qualitative data (e.g. performance status) and quantitative data (e.g. weight) will be summarized by appropriate descriptive statistics for each treatment cohort in Phase Ib and for each group in Phase II.

10.3 Treatments (study treatment, concomitant therapies, compliance)

For each of MCS110 and PDR001, the actual dose and duration in days of treatment as well as the dose intensity (actual dose received/actual duration) and relative dose intensity (the ratio of dose intensity to planned dose/planned duration) will be listed and summarized by means of descriptive statistics by treatment group. Categories for relative dose intensity of MCS110 or PDR001 will be specified as < 0.5 , $\geq 0.5 - < 0.75$, $\geq 0.75 - < 0.9$, $\geq 0.9 - < 1.1$ and ≥ 1.1 . The number and proportion of patients within each category will be presented by treatment group.

Concomitant medications and significant non-drug therapies prior to and after the start of the study treatment will be listed by patient and summarized by ATC term and treatment group.

The reason for discontinuation from treatment will be summarized and listed, along with dates of first and last dose of MCS110 and PDR001 (if applicable), duration of exposure to MCS110 and PDR001 (if applicable) and date of discontinuation for each patient.

Compliance with the protocol will be assessed by the number and proportion of patients with protocol deviations. Protocol deviations will be identified prior to database lock and will be listed and summarized.

10.4 Primary objective

Phase Ib

The primary objective of the Phase Ib part is to characterize the safety and tolerability of MCS110 given in combination with PDR001 and to identify a recommended dose for Phase II.

Phase II

The primary objective of the Phase II part of this study is to estimate the anti-tumor activity of the combination of MCS110 with PDR001 in each expansion group.

10.4.1 Variable

Phase Ib

The primary variables of Phase Ib are:

- Safety: Incidence and severity of AEs and SAEs, including changes in laboratory values, vital signs, and ECGs;
- Tolerability: Dose interruptions, reductions, and dose intensity;
- Incidence of DLTs in the first two cycles of study treatment

Phase II

For TNBC, endometrial carcinoma and melanoma the primary variable of Phase II is the Overall Response Rate (ORR), defined as the proportion of patients with a best overall response of complete response (CR) or partial response (PR) based on local Investigator assessment, as defined in RECIST v1.1. Estimation of the true ORR in this part of the study will be based upon the observed BOR for patients in the FAS, using a Bayesian analysis.

For pancreatic patients, the primary variable of Phase II is the Clinical Benefit Rate (CBR), defined as the proportion of patients with a best overall response of complete response (CR) or partial response (PR) (with at least two assessments 4 weeks apart) or stable disease (SD) > 4 months based on local Investigator assessment, as defined in RECIST v1.1.

10.4.2 Statistical hypothesis, model, and method of analysis

10.4.2.1 Phase Ib

10.4.2.1.1 Identification of a recommended dose

The dose escalation part of this study will be guided by a Bayesian analysis of first two cycles dose limiting toxicity (DLT) data for MCS110 and PDR001 in combination. The Bayesian analysis will be based on a model with three parts, representing:

- Single agent MCS110 : $\text{logit}(\pi_1(d_1)) = \log(\alpha_1) + \beta_1 \log(d_1/d_1^*)$; $d_1^* = 5 \text{ mg/kg Q3W}$
- Single agent PDR001: $\text{logit}(\pi_2(d_2)) = \log(\alpha_2) + \beta_2 \log(d_2/d_2^*)$; $d_2^* = 300 \text{ mg Q3W}$
- Interaction: $\text{Odds}(\pi_{12}(d_1, d_2)) = \pi_{12}(d_1, d_2) / (1 - \pi_{12}(d_1, d_2))$

$$= \exp(\eta(d_1/d_1^*)(d_2/d_2^*))(\pi_1(d_1) + \pi_2(d_2) - \pi_1(d_1)\pi_2(d_2)) / ((1 - \pi_1(d_1))(1 - \pi_2(d_2))),$$

where $\text{logit}(\pi.(d.)) = \log[\pi.(d.) / \{1 - \pi.(d.)\}]$, $d_1^* = 5 \text{ mg/kg}$ and $d_2^* = 300 \text{ mg}$ are the reference doses of MCS110 and PDR001 respectively, $\alpha_1, \alpha_2, \beta_1, \beta_2 > 0$ and $-\infty < \eta < \infty$.

Single agent toxicity is modelled using logistic regression for the probability of a patient experiencing a DLT against log-dose. The odds of a DLT are then calculated under no interaction for the two single agent toxicities, and interaction is accounted for by adjusting these odds with an additional model parameter (odds multiplier). Details of the model are given in ([Appendix 3](#)).

Assessment of patient risk

After each cohort of patients, the posterior distribution for the risk of DLT for new patients at combination doses of interest will be evaluated. The posterior distributions will be summarized to provide the posterior probability that the risk of DLT lies within the following intervals:

Under-dosing:	[0 , 0.16]
Targeted toxicity:	[0.16 , 0.33]
Excessive toxicity:	[0.33 , 1]

The escalation with overdose control (EWOC) principle

Dosing decisions are guided by the escalation with overdose control principle ([Rogatko 2007](#)). A combination dose may only be used for newly enrolled patients if the risk of excessive toxicity at that combination dose is less than 25%.

Prior distributions

For each single agent model, a mixture prior was derived. For MCS110, this study uses a mixture prior consisting of two components. Component 1 is the distribution derived based on dose-DLT data. The assigned weight for Component 1 is 80%. Component 2 allows for a higher toxicity case. The assigned weight for Component 2 is 20%. For PDR001, this study uses a mixture prior consisting of three components. Component 1 and 2 are derived based on dose-DLT data. The assigned total weight for Component 1 and 2 is 80%. Component 3 allows for a higher toxicity case. The assigned weight for Component 3 is 20%.

A meta-analytic-predictive (MAP) approach was used to derive Component 1 of the prior distribution for the single agent MCS110 model parameters, and Component 1 and 2 of the prior distribution for the single agent PDR001 model parameters. The MAP prior for the logistic model parameters for this study is the conditional distribution of the parameters given the historical data (see [Spiegelhalter 2004](#), [Neuenschwander 2010](#), [Neuenschwander 2014](#)). MAP priors are derived from hierarchical models, which take into account possible differences between the studies.

For this study, available clinical data were taken from the following clinical studies:

For MCS110: [\[CMCS110A2101\]](#) first-in-human MCS110 study. This study is completed. [\[CMCS110X2201\]](#) a Phase II study in PVNS patients. This study is ongoing.

For PDR001: [\[CPDR001X2101\]](#) first-in-human PDR001 oncology study. This study is ongoing.

For each of the single agent prior, an additional high toxic component is introduced to allow for a higher toxicity case. A full description of the application of the MAP approach to derive the prior distributions of the single agent MCS110 and PDR001 model parameters is given in ([Appendix 3](#))

The prior distribution for the interaction parameter was based upon prior understanding of possible drug safety interactions ([Section 1.3.3](#)). This prior allows for the possibility of either synergistic or antagonistic interaction, and is fully described in ([Appendix 3](#)).

Starting dose

The starting dose is 3 mg/kg for MCS110, and 100 mg for PDR001 which will be administered every 3 weeks (see [Section 6.2.1](#)). For this dose the prior risk of excessive toxicity is 10.4%, which satisfies the EWOC criterion. A full assessment of the prior risk to patients is given in ([Appendix 3](#)). Before first patient first visit (FPFV), the BLRM will be updated with additional PDR001 single agent data (if available) to ensure the starting dose still satisfies EWOC.

Listing of DLTs

DLTs will be listed, and their incidence summarized by primary system organ class and worst grade (CTCAE version 4.03). Listings and summaries will be based on the DDS.

10.4.2.1.2 Safety analyses

Analyses set and grouping for the analyses

For all safety analyses, the safety set will be used. All listings and tables will be presented by treatment group.

The overall observation period will be divided into three mutually exclusive segments:

1. pre-treatment period: from day of patient's informed consent to the day before first dose of study treatment
2. on-treatment period: from day of first dose of study medication to 30 days after the last dose of study treatment

3. post-treatment period: from 31 days after date of last administration of study treatment

Safety summaries will primarily be based on all data from the on-treatment period. Following last administration of study treatment, adverse events (including serious adverse events), and new antineoplastic therapies are collected for a period of 150 days. Following start of new antineoplastic therapy, only treatment related adverse events will be collected. Select summaries of related adverse events will be produced for the combined on-treatment and post-treatment periods for patients receiving PDR001.

Adverse events (AEs)

Summary tables for AEs have to include only AEs that started or worsened during the on-treatment period, the treatment-emergent AEs. However, all safety data (including those from the pre and post-treatment periods) will be listed and those collected during the pre-treatment and post-treatment period are to be flagged.

The incidence of treatment-emergent AEs (new or worsening from baseline) will be summarized by system organ class and or preferred term, severity (based on CTCAE grades), type of AE, relation to study treatment by treatment group.

Deaths reportable as SAEs and non-fatal SAEs will be listed by patient and tabulated by type of AE and treatment group.

Specific safety event categories (SEC) may be considered. Such categories consist of one or more well-defined safety events which are similar in nature and for which there is a specific clinical interest in connection with the study treatment(s), which is specified in case retrieval strategy (CRS). SEC will be specified in the statistical analysis plan (SAP) and finalized prior to database lock.

For each specified SEC, number and percentage of patients with at least one event part of the SEC will be reported.

Laboratory abnormalities

For laboratory tests covered by the Common Terminology Criteria for Adverse Events (CTCAE) version 4.03 the study's biostatistical and reporting team will grade laboratory data accordingly. For laboratory tests covered by CTCAE, a Grade 0 will be assigned for all non-missing values not graded as 1 or higher. Grade 5 will not be used.

For laboratory tests where grades are not defined by CTCAE, results will be graded by the low/normal/high classifications based on laboratory normal ranges.

The following by-treatment summaries will be generated separately for hematology, biochemistry and urinary laboratory tests:

- Frequency table for newly occurring on-treatment grades 3 or 4 (see below for details).
- Shift tables using CTCAE grades to compare baseline to the worst on-treatment value.
- Listing of all clinically relevant laboratory data with values flagged to show the corresponding CTCAE grades and the classifications relative to the laboratory normal ranges.

In addition to the above mentioned tables and listings, [REDACTED] analyses may be specified in the SAP.

ECG

- shift table baseline to worst on-treatment result for overall assessments
- listing of ECG evaluations
- listing of ECG evaluations for all patients with at least one abnormality

Vital signs

Definitions of notably abnormal results will be specified in the SAP.

- Listing of vital signs
- shift table baseline to worst on-treatment result

10.4.2.1.3 Tolerability

Tolerability of study treatment will be assessed by summarizing the number of treatment dose interruptions and dose reductions. Reasons for dose interruptions and dose reductions will be listed by patient and summarized ([Section 10.3](#)).

10.4.2.2 Phase II

A Bayesian design will be used in order to estimate ORR (Group 1, 3 and 4) or CBR (Group 2) for each of the following groups in the Phase II part of the study.

- Group 1: MCS110+PDR001, TNBC (naïve to PD-1/PD-L1 directed therapy)
- Group 2: MCS110+PDR001, Pancreatic adenocarcinoma (naïve to PD-1/PD-L1 directed therapy)
- Group 3: MCS110+PDR001, Endometrial carcinoma (naïve to PD-1/PD-L1 directed therapy)
- Group 4: MCS110+PDR001, Melanoma (progressed on previous PD-1/PD-L1 therapy)

Groups 1, 3 and 4 will enroll approximately 20 patients, and may be extended to approximately 40 patients (if at least 3 patients have an objective response for Group 1 and 3; and if at least 2 patients have an objective response for Group 4). In Group 2, 20 patients will be enrolled at RP2D, and enrollment may be extended to approximately 40 patients if clinical benefit is observed in at least 3 pts. In addition, an exploratory group of 20 patients at a lower dose (1 mg/kg MCS110 in combination with PDR001 300 mg) may be opened if the above mentioned gating criterion is met (Group 2b). See timing of the decision-making in [Section 4.2](#). The primary analysis will be performed when all patients have completed at least 6 cycles of treatment or discontinued prior to that time for any reason.

Group 1, 3: Minimally informative unimodal Beta prior distribution is defined such that the prior mean ORR is set to be equal to 30% and the parameters of the minimally informative Beta prior distribution of ORR have been set up as following:

- $a/(a+b) = 0.3$
- $a = 0.43$

- $b = 1$.

At primary analysis, this prior distribution will be updated with all the data available from the patients in the FAS. See sample size estimation in [Section 10.8](#).

Once updated, the estimate ORR and probability of ORR lies in the following categories will be reported:

- [0%, 15%) unacceptable efficacy
- [15%, 30%) moderate efficacy
- [30%, 100%] clinically relevant efficacy

If the observed ORR is equal to or greater than 30% (i.e. ≥ 12 responses (CR or PR) of out 40 patients) then this will be considered as preliminary evidence of antitumor activity of MCS110+PDR001 in the respective patient group naive to PD-1/PD-L1 directed therapy.

Note that, for a sample size of $n = 40$, if the observed ORR is 30% then the posterior probability of true ORR greater than 20% is 93.0%.

Group 2: Minimally informative unimodal Beta prior distribution is defined such that the prior mean CBR is conservatively set to be equal to 15% and the parameters of the minimally informative Beta prior distribution of CBR have been set up as following:

- $a/(a+b) = 0.15$
- $a = 0.18$
- $b = 1$.

At primary analysis, this prior distribution will be updated with all the data available from the patients in the FAS. See sample size estimation in [Section 10.8](#).

If the lower MCS110 dose level is explored (Group 2b), a separate model with the same prior assumption will be used to estimate CBR.

Once updated, the estimate CBR and probability of CBR lies in the following categories will be reported:

- [0%, 7.5%) unacceptable efficacy
- [7.5%, 15%) moderate efficacy
- [15%, 100%] clinically relevant efficacy

Observed CBR will be analyzed by dose level. If the observed CBR is equal to or greater than 15% (i.e. ≥ 6 responses (CR, or PR, or SD for at least 4 months) out of 40 patients at RP2D; or ≥ 3 responses (CR, or PR, or SD for at least 4 months) out of 20 patients at lower dose group (Group 2b) then this will be considered as preliminary evidence of antitumor activity of MCS110+PDR001 in the pancreatic patient group naive to PD-1/PD-L1 directed therapy.

Note that, for a sample size of $n = 40$, if the observed ORR is 15% then the posterior probability of true CBR greater than 7.5% is 93.5%; for a sample size of $n = 20$, if the observed ORR is 15% then the posterior probability of true CBR greater than 7.5% is 84.3%.

Group 4

Minimally informative unimodal Beta prior distribution is defined such that the prior mean ORR is conservatively set to be equal to 15% and the parameters of the minimally informative Beta prior distribution of ORR have been set up as following:

- $a/(a+b) = 0.15$
- $a = 0.18$
- $b = 1$.

At primary analysis, this prior distribution will be updated with all the data available from the patients in the FAS. See sample size estimation in [Section 10.8](#).

Once updated, the estimate ORR and probability of ORR lies in the following categories will be reported:

- [0%, 7.5%) unacceptable efficacy
- [7.5%, 15%) moderate efficacy
- [15%, 100%] clinically relevant efficacy

If the observed ORR is equal to or greater than 15% (i.e. ≥ 6 responses (CR or PR) of out 40 patients) then this will be considered as preliminary evidence of antitumor activity of MCS110+PDR001 in the respective patient group resistant to PD-1/PD-L1 directed therapy.

Note that, for a sample size of $n = 40$, if the observed ORR is 15% then the posterior probability of true ORR greater than 7.5% is 93.5%.

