The screening period begins once the patient has signed the study informed consent. Patients will be evaluated against study inclusion and exclusion criteria ([Table 7-1](#) and [Section 5.2](#), [Section 5.3](#) and [Section 7.1.1](#)).

Treatment period

The treatment period will begin on Cycle 1 Day 1. For the purpose of scheduling and evaluations, a treatment cycle will consist of 21 days.

Further details are provided in [Table 7-1](#) and [Section 7.1.2](#).

Follow-up (FU) period

Patients will be followed up for safety evaluations 150 days after the last administration of PDR001. For patients who had to stop PDR001 treatment but continued taking MCS110 at the time of treatment stop, the follow-up evaluation will take place 90 days after the last administration of MCS110 or 150 days after the last administration of PDR001, whichever duration is longer ([Table 7-1](#) and [Section 7.1.5](#)).

Disease progression FU

Patients who discontinue study treatment for any reason other than disease progression as per irRC will be followed up for progression of disease ([Section 7.1.5](#)). The disease progression follow-up will be performed until all patients enrolled in the Phase II part of the study have had progression of disease or discontinued the study for any reason.

Survival FU

Patients enrolled in Phase Ib and Phase II part will be followed for survival ([Section 7.1.5](#)) until the end of the study is reached, unless patients withdraw consent or are lost to follow-up.

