4.2 Timing of interim analyses and design adaptations

No formal interim analyses are planned in the study. However, in the Phase Ib part, the dose-escalation design foresees that decisions based on the current data are taken before the end of the study. In the Phase II part the number of patients with tumor response will be monitored in each disease group to decide if the enrollment should be extended (see [Section 2.2](#), [Section 4.1](#) and [Section 10.7](#)). The decision of whether to expand a certain group will be made at the time when at least 3 patients, for Group 1 or 3, or at least 2 patients for Group 4 have an objective response (CR or PR) per RECIST v1.1 or irRC, or the last patient has been on treatment for at least 6 months, whichever occurs earlier. For Group 2, the decision to expand will be made if clinical benefit per RECIST v1.1 or irRC (CR, PR or SD > 4 months) is observed in at least 3 patients or the last patient has been on treatment for at least 6 months. The decision to extend enrolment will be made separately for each of the groups.

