7.1 Study flow and visit schedule

[Table 7-1](#) lists all of the assessments and indicates with an “X”, the visits when they are performed. All data obtained from these assessments must be supported in the patient’s source documentation. The table (“Category” column) indicates which assessments produce data to be entered into the clinical database (D) or remain in source documents only (S).

No CRF will be used as a source document.

Screening/baseline evaluations must be performed ≤ 21 days before Cycle 1 Day 1, except for baseline radiological evaluations which must be done within 28 days. Assessments performed as part of the screening evaluations and within 3 days prior to the first dose of study treatment, are not required to be repeated on the first dosing day.

Laboratory and radiological assessments performed as part of standard of care prior to signing informed consent may be used if performed within 21 days and 28 days respectively, of Cycle 1 Day 1.

During the course of the study visits, test and/or procedures should occur on schedule whenever possible. A visit window of ± 7 days is allowed. If the infusion of MCS110 and/or PDR001 is delayed, the visits assessments will be shifted accordingly. On PK collection days the windows are provided in [Section 7.2.3](#).

Radiological assessments must be performed ± 1 week of the scheduled date of the assessment.

For Japan only, patients are required to be hospitalized during Cycle 1.

Visit name	Category	Protocol Section	Screening Phase	Treatment Phase														Follow-up	Disease Progression F/U	Survival F/U	
			Screening	Cycle 1					Cycle 2		Cycle 3	Cycle 4					Subsequent cycles	EOT			Safety F/U
Day of cycle			-21 to -1	1	2	4	8	15	1	15	1	1	2	4	8	15	1				
Prior/concomitant medications, surgery and medical procedures	D	7.1.1.2 7.1.5 and 6.4	X	Continuous ¹																	
Physical examination	S	7.2.2.1	X	X			X	X	X	X	X	X					X	X			
Height	D	7.2.2.3	X																		
Weight	D	7.2.2.3	X	X					X		X	X					X	X			
Vital signs	D	7.2.2.2	X	X			X	X	X	X	X	X					X	X			
Performance status	D	7.2.2.4	X	X					X		X	X					X	X			
Hematology	D	7.2.2.5.1	X	X			X	X	X	X	X	X			X		X	X			
Chemistry	D	7.2.2.5.2	X	X			X	X	X	X	X	X			X		X	X			
Coagulation	D	7.2.2.5.6	X	Only if clinically significant														X			
Urinalysis	D	7.2.2.5.3	X	X					X		X	X					X	X			
Thyroid function	D	7.2.2.5.4	X	X					X		X	X					X	X			

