7.2 Assessment types

7.2.1 Efficacy assessments

Tumor response will be determined locally according to two sets of criteria:

1. RECIST v1.1 ([Appendix 1](#))
2. irRC ([Appendix 2](#))

The local investigator's assessment will be used for the analysis of response according to both RECIST v1.1 and irRC, and for treatment decision making (study discontinuation due to PD is per irRC). During the course of the study, Novartis may decide to have a central review of the radiological assessments performed. In such case, the investigator's staff will be instructed on how to send data from these radiological assessments to a Contract Research Organization (CRO) for central review when needed.

At screening, all patients will undergo CT with i.v. contrast of the chest, abdomen and pelvis. If there is clinical evidence of disease in the neck, a CT with i.v. contrast of the neck will also

be performed. MRI should only be used to evaluate sites of disease that are not adequately imaged by CT. If a patient is intolerant of iodine-based contrast agents, CTs may be performed without contrast. MRI may be used to evaluate sites of disease where a CT without i.v. contrast is not adequate. Visible skin lesions and easily palpable subcutaneous tumors may be measured by physical examination using a ruler or calipers. Ultrasound should not be used to measure sites of disease. See [Table 7-2](#) for further details.

Tumor assessments will be performed at the following time points until progression of disease per irRC or patient withdrawal:

- Screening
- Every 2 cycles from Cycle 3 Day 1 up to Cycle 9 Day 1, then every 3 cycles until Cycle 18 Day 1 (1 year of treatment). Assessment will be performed every 4 cycles thereafter, starting from Cycle 22 Day 1.
- At the End of Treatment, if a scan was not conducted within 30 days prior to End of Treatment
- After EOT, during disease progression follow-up, every 9 weeks (\pm 1 week) until week 51, then every 12 weeks (\pm 1 week), until progression of disease per irRC.
- PR or CR, per both RECIST v1.1 and irRC, will be confirmed by a new assessment after at least 4 weeks. Also Progressive Disease (PD), as per irRC, will be confirmed after at least 4 weeks.

If available, tumor markers collected as per local guidelines will be collected at the same time as RECIST tumor evaluation.

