2.4.1 Study treatment/compliance

Study treatment

MCS110 in combination with PDR001 (Q3W):

- Last date of *exposure* to study drug (MCS110) = last date of administration of MCS110 + 20 days
- Last date of *exposure* to study drug (PDR001) = last date of administration of PDR001 + 20 days
- Last date of *exposure* to study treatment (MCS110 + PDR001) = max (last date of MCS110 administration, last date of PDR001 administration) + 20 days = Date of last administration of study treatment + 20 days

Planned treatment: Planned treatment is the treatment to which a patient is assigned during enrollment.

Received treatment: Please refer to [Section 2.2.2](#).

Planned dose: Planned dose is the dose level(s) of study drug(s) corresponding to the planned treatment.

Prescribed dose: Prescribed dose is the dose level(s) of study drug(s) prescribed by doctor before study treatment is administered at beginning of each cycle.

Dose administered (mg/kg) for MCS110 = Dose prescribed (mg/kg) * Total volume administered (mL)/Total volume planned to be administered (mL);

Dose administered (mg) for PDR001 = Dose prescribed (mg) * Total volume administered (mL)/Total volume planned to be administered (mL);

Definitions of duration of exposure, cumulative dose, actual dose intensity (DI), planned dose intensity (PDI), relative dose intensity (RDI), as well as intermediate calculations, are as follows:

- **Duration of exposure (days) to study drug:** last date of *exposure* to study drug – first date of study drug + 1 (periods of interruption are not excluded);

- **Duration of exposure (days) to study treatment:** last date of *exposure* to study treatment – first date of study treatment + 1 (periods of interruption are not excluded);
- **Duration of exposure (weeks)** = Duration of exposure (days)/7;
- **Cumulative dose:** sum of all dose administered (mg/kg) to a patient for MCS110; sum of all dose administered (mg) to a patients for PDR001;
- **Cumulative planned dose:** sum of all planned dose (mg/kg) of MCS110 that were intended to have been taken during the treatment period by a patient; sum of all planned dose (mg) of PDR001 that were intended to have been taken during the treatment period by a patient;

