2.5.2.2 Phase II part

A Bayesian design will be used in order to estimate ORR (Group 1, 3 and 4) or CBR (Group 2) for each of the following groups in the Phase II part of the study.

- Group 1: MCS110 + PDR001, TNBC (naïve to PD-1/PD-L1 directed therapy)
- Group 2: MCS110 + PDR001, Pancreatic adenocarcinoma (naïve to PD-1/PD-L1 directed therapy)
- Group 3: MCS110 + PDR001, Endometrial carcinoma (naïve to PD-1/PD-L1 directed therapy)
- Group 4: MCS110 + PDR001, Melanoma (progressed on previous PD-1/PD-L1 therapy)

Each group will enroll approximately 20 patients, and may be extended to 40 patients (if at least 3 patients have an objective response for group 1, 2 and 3; and if at least 2 patients have an objective response for group 4). In addition, an exploratory group of 20 patients at a lower dose (1 mg/kg MCS110 in combination with PDR001 300 mg) may be opened if at least 3 patients have an objective response for group 2. See timing of the decision-making in [CMCS110Z2102-CSP-Section 4.2]. The primary analysis will be performed when all patients have completed at least 6 cycles of treatment or discontinued prior to that time for any reason.

Group 1, 3: Minimally informative unimodal Beta prior distribution are defined such that the prior mean ORR is set to be equal to 30% and the parameters of the minimally informative Beta prior distribution of ORR have been set up as following:

- $a/(a + b) = 0.3$
- $a = 0.43$
- $b = 1$.

At primary analysis, this prior distribution will be updated with all the data available from the patients in the FAS. Once updated, the estimate ORR and probability of ORR lies in the following categories will be reported:

- [0%, 15%] unacceptable efficacy
- [15%, 30%] moderate efficacy
- [30%, 100%] clinically relevant efficacy

If the observed ORR is equal to or greater than 30% (i.e. ≥ 12 responses (CR or PR) of out 40 patients) then this will be considered as preliminary evidence of antitumor activity of MCS110 + PDR001 in the respective patient group naive to PD-1/PD-L1 directed therapy.

Group 2: Minimally informative unimodal Beta prior distribution is defined such that the prior mean CBR is conservatively set to be equal to 15% and the parameters of the minimally informative Beta prior distribution of CBR have been set up as following:

- $a/(a + b) = 0.15$
- $a = 0.18$
- $b = 1$.

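### The primary-analysis trigger of six completed cycles ends on day 126 and does not secure the Cycle 7 Day 1 scan, the first scheduled scan that can establish Group 2's stable disease beyond 4 months

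*Protocol*

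**What the plan says.** **Trigger.** Protocol Section 10.4.2.2 states: "The primary analysis will be performed when all patients have completed at least 6 cycles of treatment"; patients who stopped earlier are exempt. SAP Section 2.5.2.2 carries the same sentence. Protocol 4.1 and 10 and SAP 1.1 and 2.1 set the same six-cycle rule for the primary report, on all Phase Ib and Phase II patients together. None of these places mentions a tumor assessment.

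**Calendar.** Protocol 4.1: "a treatment cycle will consist of 21 days". Protocol 7.2.1 schedules scans "Every 2 cycles from Cycle 3 Day 1 up to Cycle 9 Day 1", and Protocol 7.1 adds: "Radiological assessments must be performed ± 1 week of the scheduled date of the assessment".

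**Endpoints.** Group 2's primary variable in Protocol 10.4.1 counts confirmed responses and "stable disease (SD) > 4 months based on local Investigator assessment"; SAP 2.7.2 gives the minimum SD duration as 16 weeks. Complete and partial responses need a second assessment at least 4 weeks later (Protocol 7.2.1 and Appendix 1).

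**Missing outcomes.** The analysis updates the prior with the data available in the FAS. SAP 2.5.3 treats an unknown or unassessed best response as failure, naming ORR only. No rule covers a patient whose SD duration or confirmation is still pending at the cut-off.

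**Expansion decision.** Under Protocol 4.2, if the required number of successes has not been reached sooner, the decision waits until "the last patient has been on treatment for at least 6 months".

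**The concern.** The trigger counts treatment cycles, but the endpoints are decided by scans, and the sixth cycle closes just before the scan that matters most for Group 2. An ongoing patient with SD at Cycle 5 Day 1 and no later scan does not meet the CBR definition, yet stays in the FAS denominator. A partial response seen once, at Cycle 5 Day 1, has a best overall response of SD until it is confirmed. Both errors run in one direction: a true success can be recorded as a failure, but not the reverse.

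The SD part is the firmer of the two, because no scheduled scan inside six cycles reaches 4 months. At stake are the estimated CBR, its posterior category probabilities, and the observed 15% threshold on which Group 2's preliminary evidence of activity rests. With 20 patients, one misclassified success is 5 percentage points.

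**Working it through.** **1. Calendar.** Day 1 of cycle k falls on day 21(k − 1) + 1, and cycle k ends on day 21k. The window is ±7 days.

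| Scan | Nominal day | Window | Weeks elapsed at nominal day |
|---|---|---|---|
| C3D1 | 43 | 36–50 | 6 |
| C5D1 | 85 | 78–92 | 12 |
| C7D1 | 127 | 120–134 | 18 |
| C9D1 | 169 | 162–176 | 24 |

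Six cycles end on day 6 × 21 = 126. SAP 2.4.1 agrees: exposure runs to the "last date of administration of MCS110 + 20 days", and a sixth dose on day 106 gives 106 + 20 = 126.

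**2. SD duration.** Four months is 4 × 30.44 = about 122 days; 16 weeks is 112 days. Day 85 is short of both, and day 127 passes both. C7D1 is therefore the first scheduled scan that can establish the endpoint under either definition. Its window straddles day 126, so at the minimum cut-off the scan may or may not be in the data. A scan on day 120 would meet 16 weeks but not 4 months.

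**3. Confirmation.** A response first seen at C5D1 can be confirmed from day 85 + 28 = 113, but the next scheduled scan is day 127. One first seen at C7D1 has its next scheduled scan on day 169.

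**4. The plan's own figure.** Protocol Table 10-4, true CBR 15%, requires at least 3 of the first 20 and at least 6 of 40. With X1 and X2 each Binomial(20, 0.15):

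P(success) = Σ over x ≥ 3 of P(X1 = x) × P(X2 ≥ 6 − x)
= 0.2428 × 0.5951 + 0.1821 × 0.8244 + 0.1028 × 0.9612 + 0.0673 × 1 = 0.461.

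This reproduces the stated 46.1%. The first-stage probability, 59.5%, also reproduces and is the Group 2b figure in Table 10-5.

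**5. Effect of missed successes.** The documents give no loss rate; 5% and 10% are assumptions. The first 20 patients enrol before the expansion decision, so the loss is applied to the second 20 only, whose success probability becomes 0.15 × 0.95 = 0.1425 or 0.15 × 0.90 = 0.135.

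- 5%: 0.2428 × 0.5578 + 0.1821 × 0.8002 + 0.1028 × 0.9538 + 0.0673 = 0.447.
- 10%: 0.2428 × 0.5188 + 0.1821 × 0.7733 + 0.1028 × 0.9450 + 0.0673 = 0.431.

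Group 2b is a single stage of 20, so P(at least 3 of 20) falls from 59.5% to 55.8% or 51.9%.

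A cruder upper bound counts k of the last 20 patients as failures whatever their true outcome. For k = 1, 3 and 6, Group 2 success is 44.7%, 41.6% and 36.2%; Group 2b success is 55.9%, 48.0% and 35.2%.

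**6. One missed success at the threshold.** The posterior is Beta(0.18 + x, 1 + n − x). The first value in each pair reproduces the plan's figure.

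| Observed | Posterior | P(CBR > 7.5%) |
|---|---|---|
| 6/40 | Beta(6.18, 35) | 93.5% |
| 5/40 | Beta(5.18, 36) | 84.3% |
| 3/20 | Beta(3.18, 18) | 84.3% |
| 2/20 | Beta(2.18, 19) | 60.4% |

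**The case against.** Several points on the other side stand.

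- **Six cycles is a minimum.** A later cut-off is allowed, and an ongoing patient who finishes cycle 6 goes straight to the C7D1 visit. This narrows the problem without removing it, since a permitted later cut-off is not a required one.
- **The one-day gap is nominal.** With the window, some C7D1 scans fall by day 126, and under the SAP's 16 weeks a scan on days 120 to 126 would qualify. Others fall on days 127 to 134.
- **Responses.** A reader might infer that a response first seen at C5D1 cannot be confirmed before the cut-off. It can, by an extra scan from day 113; C7D1 is only the next scheduled one. Any finite cut-off also leaves some late first responses unconfirmed.
- **Scope.** A reader might infer that the last six weeks of enrolment in every group are exposed. There is one study-wide trigger, so groups that filled earlier gain follow-up. Only patients late in the whole study's enrolment, still on treatment and undecided, are exposed.
- **Comparison with the expansion rule.** Six months is the latest point for that decision. Protocol 4.2 (Groups 1, 3 and 4) and Protocol 10.7 (all groups) let it come earlier once enough successes are seen, so it does not set a uniform six-month standard.
- **Final report.** Later data go into a final CSR, but neither document says that the primary Bayesian analysis will be repeated there.
- **Trial as run.** Amendment 05 reports that no group met its expansion criterion and that the last patient was enrolled on 10-Jan-2019. By 08-Jul-2019 that patient was on day 180, or day 159 if dosing began 21 days after enrolment, past nominal C7D1 either way.

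**Conclusion.** The point holds as a gap in the specified timing. The trigger guarantees day 126 and the C5D1 scan, while Group 2's SD criterion needs C7D1. The resulting bias is downward; it is firm for CBR and weaker for ORR, where an earlier confirmatory scan is possible.

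The size is modest. Under the assumed 5% or 10% loss in the second 20, Group 2 success at true CBR 15% falls by 1.4 or 3.0 points (46.1% to 44.7% or 43.1%). Group 2b, where all 20 patients could be exposed, falls by 3.7 or 7.6 points (59.5% to 55.8% or 51.9%). A single missed success matters most at the decision boundary. No figure is put on ORR, because it depends on when responses first appear and whether extra scans are taken.

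Applying the same loss to all 40 patients and to the expansion decision would give 41.3% or 36.4%. The documents do not support that reading: the first 20 would be well past C7D1 by the primary cut-off, and the expansion decision has its own timing.

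Nor do the documents show that anyone was misclassified. The actual cut-off date is not stated, no group was expanded, and Group 2b's opening depended on the same Group 2 criterion. The 40-patient and Group 2b probabilities therefore describe the design, not this trial's result.

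**What to change.** In Protocol 4.1, 10 and 10.4.2.2 and SAP 1.1, 2.1 and 2.5.2.2, tie the primary cut-off to a scan: every patient still on study has had the C7D1 assessment, window included, which means day 134 or later for the last patient. A cut-off at C9D1 plus window (day 176), or 6 months from first dose (about day 183), would also let a response first seen at C7D1 be confirmed at its next scheduled scan. Choosing between these is a matter of preference; C7D1 plus window is the minimum that closes the SD gap.

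The cost is wording and a later cut-off: 134 − 126 = 8 days, 176 − 126 = 50 days, or 183 − 126 = 57 days, so about 1 to 8 weeks. If the actual cut-off was already late enough, stating its date and the minimum scan follow-up of ongoing patients in the SAP or CSR settles the matter at no cost in time.
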